### 5.2.4 Baseline Values

Baseline values that are missing will not be imputed for safety or efficacy measures. For efficacy assessments scheduled to be collected at more than one visit during the Screening/Baseline period, the baseline value will be based on the average of all nonmissing values from assessments conducted prior to the first dose of study drug. For assessments scheduled to be collected once during the Screening/Baseline period, the value from the most recent non-missing assessment prior to the first dose will be used. For safety and other assessments, the value from the most recent non-missing assessment prior to the first dose will be used.

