9. STUDY PROCEDURES

9.1 Overview of Study Visits

The Screening/Baseline period will be conducted over 4 to 6 weeks. The second visit during the Screening/Baseline period (Visit 2) should be conducted 2 weeks \pm 1 day after the Screening visit (Visit 1). The participant will then remain in Screening for an additional 2 to 4 weeks. The caregiver diary must be completed daily during the entire Screening/Baseline period whether it is 4 weeks or 6 weeks. The Screening visit (Visit 1) and Baseline visit (Visit 3) may be conducted over three consecutive days. It is preferrable that ECGs, safety labs and biomarker sample collection are conducted on the same day. No assessments can be conducted until informed consent has been given by the caregiver or legally authorized representative. Also, training for the caregivers on all caregiver completed assessments must be completed before the caregiver rater may complete the assessments. All assessments must be completed within the window for the visit, as shown in the Schedule of Assessments in Section 4. For Visit 3, all assessments must be completed before administration of the IMP.

The in-clinic visits will be conducted in person at the study site. As described below, safety and efficacy assessments will be completed by site personnel. The caregiver will also complete caregiver assessments the day of the visit or the day before the visit as described below (except the caregiver diary which is completed daily), and these will be reviewed by site personnel. In-clinic visits will be done at Screening (Visit 1), Baseline (Visit 3), Week 2 (Visit 5), Week 6 (Visit 9), and Week 13 (EOT, Visit 16). For all visits designated as in-clinic (Visits 1, 3, 5, 9 and 16), an in-person visit is preferred. Off-site assessments may be allowed due to extenuating circumstances due to the COVID-19 health emergency. All requests for off-site assessments must be approved in advance by the Sponsor or Medical Monitor.

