9.5.9.2 Clinical Global Impression of Improvement (CGI-I)

Clinical Global Impression of Improvement assessments will be made at Visit 9 (Week 6), EOT (Week 13, Visit 16), and Follow-up (Week 15, Visit 17). The CGI-I scale³⁶ requires the Investigator to rate how much the participant's illness has improved or worsened relative to a baseline state. A 7-point scale is used with the following values: 1, very much improved; 2, much improved; 3, minimally improved; 4, no change; 5, minimally worse; 6, much worse; 7, very much worse. The CGI-I will be evaluated using PTHS-specific scoring anchors. The clinicians will provide an overall global improvement rating and an improvement rating for each of seven domains: language/communication, social initiation/social avoidance, fine motor functioning/self-help challenging behavior, ambulation/gross motor, gastrointestinal issues, and autonomic/breathing abnormalities. The clinician should assess the participant's current state taking into consideration observations at the visit and symptoms within the last week. The rating of change is compared with status at Baseline (Visit 3). To ensure that interpretation of the scoring rubric is normalized among the raters, clinicians administering the CGI-I will be required to complete scoring calibration training.

9.5.9.3 Bayley Scales of Infant Development v4 (BSID4) or Stanford-Binet Intelligence Scales v5 (SB5)

The Stanford-Binet Intelligence Scales version 5 (SB5) assessment will be done at Screening (Visit 1) and EOT (Week 13, Visit 16). SB5 is validated for ages 2 to 85+ and measures both verbal and nonverbal intellectual and cognitive abilities through a set of 10 subtests. The General cognitive ability is reported as a full-scale intellectual quotient score (FSIQ). Cognitive ability in five categories are reported in the index scores: fluid reasoning (FR), knowledge (KN), quantitative reasoning (QR), visual-spatial processing (VS), and working memory (WM). Non-verbal (NVIQ) and verbal intelligence quotients (VIQ) are also calculated. Scoring of index scores and IQ will be calculated using the z-deviation method for intellectual disability.

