11.3 Efficacy Analysis

Efficacy will be assessed by looking at within-participant changes from the Baseline period to the EOT using the efficacy endpoints listed in Section 6.3.2.

The participant's baseline characteristics and symptom severity will be established based on assessments collected during the 4 to 6 week Screening/Baseline period. Baseline values will be based on the average values of visits 1, 2, and 3 for assessments collected at more than one visit. A Wilcoxon signed rank test will be used to test for improvement and an exact significance level will be computed.

Potentially influential factors will be considered and addressed with a linear regression model. This model may include covariates such as age, sex, nonverbal NVIQ or NVIQ equivalent, genotype, history of regression (yes/no), ASD diagnosis (yes/no) with no more than two covariates included in any model. Descriptive statistics and corresponding graphics will be used to present the results. The safety and efficacy analysis details will be specified in the SAP.

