A correlation analysis of the efficacy measures will be done using Pearson correlation coefficients at Baseline and EOT. The correlation of each total score will be measured against the others and presented in a table and a heat map/matrix. CGI-I and CGI-S domain scores will also be included in the correlation analysis. Test-retest reliability will be assessed for continuous efficacy assessments collected more than once during the Screening period (Visits 1, 2, and 3, pre-dosing) using Intraclass Correlation Coefficients

Statistical Analysis Plan 30APR2024

(ICC). The ICC will be based on covariance parameter estimates from a Restricted Maximum Likelihood Mixed Model including results from assessments conducted during the Screening/Baseline period with a random effect for subject. The ICC will be derived as: ICC = Within-subject covariance/Total covariance. ICC values range from 0 to 1, with values closer to 1 indicating greater test-retest reliability.

A treatment policy estimand will be used for all endpoints. The variables of interest are numeric scores associated with subject responses. Summaries will be performed on the observed data. There will be no imputations for completely missing scores or intercurrent events. Handling of missing responses items that contribute to total and subscale scores are defined in Section 5.2.5.

Results for each efficacy variable will also be listed by subject.

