### 9.2.4 Clinical Global Impression Scale - Severity - Overall Severity Score

Clinical Global Impression of Severity assessments will be made at the Screening visit (Visit 1), Visit 3 (Week 0), Visit 9 (Week 6), End of Treatment (Week 13, Visit 16), and Follow-up (Week 15, Visit 17). The overall severity score is scored on a 7-point scale, where 1='typical for age, not at all impaired'; 2='borderline, slightly impaired'; 3='mildly impaired'; 4='moderately impaired'; 5='markedly impaired'; 6='severely impaired'; 7='among the most severely impaired'. Lower scores reflect less impairment. Within subject change is the difference between the score at each relevant follow-up visit and the score at baseline. If a score is missing, the subject will be excluded from the corresponding summaries.

The overall score and change from baseline at each post-baseline visit will be summarized using descriptive statistics. Within subject changes will be analyzed using a Wilcoxon signed rank test at Week 6 and EOT. Test-retest reliability will be assessed for all scores collected during the Screening period (Visits 1 and 3) using ICC. The change from baseline in the overall score at EOT will be presented in figures as described in Section 9.2. The overall score will also be presented as a line graph at post-baseline visits.

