#### 9.2.9 Aberrant Behavior Checklist-2 Scores

The ABC-2 will be completed at all Screening/Baseline period visits (Visits 1, 2, 3), as well as Week 6 (Visit 9), End of Treatment (Week 13, Visit 16), and Follow-up (Visit 17). Each item is scored on a 4-point scale, where 0= Not at all a problem; 1= The behavior is a problem but slight in degree; 2= The problem is moderately serious; 3= The problem is severe in degree. The items are grouped into 5 subscales: Irritability (Subscale I, score ranges from 0 - 45), Social Withdrawal (Subscale II, score ranges from 0 - 48), Stereotypic Behavior (Subscale III, score ranges from 0 - 21), Hyperactivity/Noncompliance (Subscale IV, score ranges from 0 - 48), and Inappropriate Speech (Subscale V, score ranges from 0 - 12). The total score has a range from 0 - 174.

Lower scores indicate fewer behavior issues. The subscale scores are calculated via a scoring algorithm in the EDC. These calculated scores will be used for the analysis. If an item is missing and as such a subscale and total score was not calculated in the EDC, the

missing items will be imputed and subscale or total scores calculated from answered and imputed items. Missing items will be imputed as defined in section 5.2.5. The total score will only be calculated if all items are answered or can be imputed. If a total score is missing after applying the imputation algorithm, then that subject will be excluded from the corresponding summaries. The subscales and their corresponding items are listed below.

- Subscale I (Irritability): Items 2, 4, 8, 10, 14, 19, 25, 29, 34, 36, 41, 47, 50, 52, 57.
- Subscale II (Social Withdrawal): Items 3, 5, 12, 16, 20, 23, 26, 30, 32, 37, 40, 42, 43, 53, 55, 58
- Subscale III (Stereotypic Behavior): Items 6, 11, 17, 27, 35, 45, 49
- Subscale IV (Hyperactivity/Noncompliance): Items 1, 7, 13, 15, 18, 21, 24, 28, 31, 38, 39, 44, 48, 51, 54, 56
- Subscale V (Inappropriate Speech): Items 9, 22, 33, 46

The subscale scores are calculated as the sum of item scores within the subscale. The total score is calculated as the sum of all items across all subscales.

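### Six repeatedly measured efficacy instruments fold the untreated run-in into their baseline, and the plan never estimates the Visit 1 to Visit 3 change

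*SAP*

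**What the plan says.** Protocol 11.3 and SAP 5.2.4 set the same rule. The protocol states: "Baseline values will be based on the average values of visits 1, 2, and 3 for assessments collected at more than one visit". The SAP states that, for efficacy measures scheduled more than once in Screening/Baseline, "the baseline value will be based on the average of all nonmissing values from assessments conducted prior to the first dose of study drug". SAP 5.2.3 also lets unscheduled screening assessments enter the baseline derivation. The SAP addendum does not revise 5.2.4.

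The schedules identify six instruments under this rule:
- Visits 1, 2 and 3: Top 3 Concerns, ABC-2, CSHQ and GIHQ.
- Visits 1 and 3: CGI-S and the modified two-minute walk test (2MWT).

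Visit 2 falls two weeks after Visit 1, and then: "The participant will then remain in Screening for an additional 2 to 4 weeks" (Protocol 9.1).

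Apart from the baseline average, the run-in values have two planned uses. One is a test-retest ICC. For CGI-S, for example: "Test-retest reliability will be assessed for all scores collected during the Screening period (Visits 1 and 3) using ICC". SAP 9.2 describes the ICC model as "including results from assessments conducted during the Screening/Baseline period with a random effect for subject" and lists no visit or time term. The other is display: line graphs by visit in SAP 9.2, specified at each visit for the four caregiver scales, plus by-subject listings. No section plans a summary or estimate of the change from Visit 1 to Visit 3.

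**The concern.** Every participant is treated (Protocol 7.3), so the run-in is the only untreated period before exposure. It is where one could see what trial entry, caregiver training, a daily diary, expectation or practice do to these scores without drug.

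Two design features make drift towards improvement plausible. CGI-S must be 4 or greater at the Screening visit (Protocol 8.1), and that selected value then enters the CGI-S baseline average. The Top 3 Concerns are chosen at Screening because they are the caregiver's priorities. Both invite regression to the mean.

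If scores improve before the first dose and then level off, the averaged baseline is worse than the participant's state at first dose. The difference appears as improvement at End of Treatment (EOT). The plan supplies no figure against which to judge it. The ICC does not fill the gap: with only a subject effect in the model, a systematic shift between visits goes into the residual and looks like poor reliability.

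At stake is the reading of the mean changes, their intervals and the signed-rank p-values for these six instruments.

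**Working it through.** **The plan's own figure.** The documents give no figure for run-in drift. Their only efficacy calculation is the detectable CGI-I difference (SAP 5.1). It reproduces with noncentral-t power at an effective n of 9 (10 × 3/π = 9.55, rounded down): effect sizes 1.067, 1.142 and 1.237, times SD 0.7, give 0.747, 0.800 and 0.866, against the stated 0.75, 0.80 and 0.87. CGI-I is rated against Visit 3, so averaging does not touch this figure.

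**Step 1. Share of run-in change counted as on-drug change.** If the true score is flat after Visit 3, the share is

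s = (V3 − mean of pre-dose values) / (V3 − V1).

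| Schedule and pattern | Calculation | s |
|---|---|---|
| Two visits (CGI-S, 2MWT) | (V3 − (V1+V3)/2)/(V3 − V1) | 0.50 |
| Three visits, linear, weeks −4, −2, 0 | 2.00/4 | 0.50 |
| Three visits, linear, weeks −5, −3, 0 | 2.67/5 | 0.53 |
| Three visits, linear, weeks −6, −4, 0 | 3.33/6 | 0.56 |
| Three visits, all change between Visits 1 and 2 | 1 − 2/3 | 0.33 |
| Three visits, all change between Visits 2 and 3 | 1 − 1/3 | 0.67 |

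With Visit 3 as baseline, s = 0.

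**Step 2. Effect on the test (illustration).** Assumptions, none of them from the documents: total SD 1, ICC 0.8 (error variance 0.2), normal errors, three visits, linear run-in improvement d followed by a plateau, and no drug effect. The test is the two-sided signed-rank test at 0.05. The spurious mean change is d/2.

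| d | Spurious change | n=10 | n=16 | n=20 |
|---|---|---|---|---|
| 0.3 SD | 0.15 SD | 13% | 17–18% | 22–23% |
| 0.5 SD | 0.25 SD | 27% | 41% | 52% |

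Ranges show the spread between repeated simulations. With Visit 3 as baseline the rate stays at about 4–5%, but that follows from setting the true EOT value equal to Visit 3.

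The result depends heavily on the assumptions. At n=10 and d=0.5 SD:
- ICC 0.5 gives 13–14%, and ICC 0.9 gives 48%.
- Front-loaded drift gives about 14%, and back-loaded drift about 43–44%.
- Adding between-subject variation in change (SD 0.5) gives 16%.

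**Step 3. If the trend does not stop at Visit 3.** With a linear trend running to Week 13 and a 4-week run-in, change from Visit 3 is 13/4 = 3.25d and change from the average is 15/4 = 3.75d. Averaging therefore adds 0.50/3.75 = 13% of the total. With a 6-week run-in it adds 0.56/2.72 = 20%. The rest arises after Visit 3, and changing the baseline does not remove it.

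**Step 4. Precision of the added analyses.** The 95% half-width for mean Visit 1 to Visit 3 change is t(0.975, n−1)/√n: 2.262/√10 = 0.72 SD of change at n=10, and 2.093/√20 = 0.47 at n=20. Under the Step 2 assumptions the SD of change is √(0.2 + 0.2/3) = 0.516 with the average and √0.4 = 0.632 with Visit 3 alone, a ratio of 1.22. For a true effect of 0.5 SD without drift at n=10, simulated power is 76% with the average and about 60% with Visit 3 alone.

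**The case against.** The case for leaving the plan alone has real substance.

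- **Averaging is pre-specified and useful.** Both documents agree on it, and it reduces baseline noise (Step 4). This stands, and it is why the averaged baseline should stay.
- **The tests carry no decision.** The SAP calls its tests descriptive (Section 5), names no primary efficacy variable (8.1) and plans no formal analysis (8.5). A reader might infer from Step 2 that the trial risks a false efficacy claim at those rates. The documents do not support that: no success criterion hangs on these p-values, and d and the ICC are assumptions. The shift in the mean change remains, however the p-value is labelled.
- **The run-in is not the only off-drug view.** A reader might take it as such, but Week 15 (Protocol 9.2.17) is off drug and repeats CGI-S, Top 3 Concerns, ABC-2, CSHQ and GIHQ. It is short and follows exposure, so it is a weak comparator and does not show pre-drug drift.
- **The trend would be visible.** Line graphs and listings would let a reader see or compute a shift on the caregiver scales. No estimate or interval is planned, and the CGI-S line graph in SAP 9.2.4 is specified for post-baseline visits.
- **Drift could go the other way.** If scores worsen in the run-in, the averaged baseline is conservative. This is true, and it is another reason to report the estimate.
- **Reference states differ across endpoints.** CGI-I and Caregiver Impression of Change are explicitly anchored to Visit 3. That is inherent in change scales and is not an error.

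**Conclusion.** The point holds for six instruments: Top 3 Concerns, ABC-2, CSHQ, GIHQ, CGI-S and 2MWT. If scores change in the run-in and then plateau, exactly half of that change enters change from baseline for CGI-S and 2MWT. For the three-visit scales the share is one third to two thirds for a monotone pattern.

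A reader might infer that half of any pre-drug improvement is counted across the efficacy endpoints. The documents do not support that. CGI-I, which drives the sample size, and Caregiver Impression of Change carry no share, nor do MB-CDI, ORCA, BPI-SF, Vineland-3, QI-Disability and ICND, whose only pre-dose value is at Visit 3. SB5/BSID-4 is a separate case: its only scheduled pre-dose value is at Visit 1, so the remedy below cannot be applied to it.

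The consequence is modest but real. The plan reports a mean change that may contain pre-drug change and gives no estimate of it. The size of the drift is not in the documents, so the percentages in Step 2 are illustrative.

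**What to change.** Keep the averaged baseline as the planned analysis. For the six instruments, add to the SAP:

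1. A descriptive summary with 95% CI of the Visit 1 to Visit 3 change, shown beside the Visit 3 to EOT change, with the unequal durations noted (4 to 6 weeks against 13 weeks).
2. A sensitivity analysis of EOT change using the Visit 3 value as baseline.
3. A statement that neither analysis removes a trend that continues after Visit 3.

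Do not turn these into a rule that calls an improvement on-treatment if it persists in (2) and exceeds the change in (1). Such a rule would pass plain drift: with a drug-free trend continuing at the same rate (4-week run-in, ICC 0.8, n=10, d=0.3 SD), about 97% of simulated trials satisfy it, taking significance in (2) and a larger mean change as the criteria.

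**Cost.** SAP wording and one extra table per instrument, from data already scheduled, with no new visits. The Visit 3 baseline is noisier, and the run-in estimate is imprecise at this size (half-width 0.72 SD of change at n=10, 0.47 at n=20). Under SAP Section 5, analyses added after database lock would be exploratory, so the change is best made before lock.

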### 5.2.5 Post-Baseline Values

For subjects who discontinue the study, data will be analyzed up to the last observation for safety and efficacy measures. Missing data for safety assessments will not be imputed. For efficacy rating scale measures other than the exceptions listed below, if an assessment has been completed but has missing items, missing values shall be imputed as follows:

- If 3 or fewer items are missing, the last observation for that particular data element (e.g., item response) will be carried forward.
- The scoring algorithms will be applied including the observed values and last observation carried forward (LOCF) for the missing items

These rules will only apply to individual items. Total scores, subdomain and subscale scores will not be carried forward. If the assessment is completely missing, items will not be imputed.

These imputation rules do not apply to the CGI-I, Clinical Global Impression Scale – Severity (CGI-S) or Caregiver Impression of Change assessments. If a particular domain is missing for these assessments, the participant will be excluded from the corresponding analysis. These imputation rules also do not apply to the Caregiver Top 3 Concerns assessment. If a concern is missing for this assessment, the average severity will still be calculated from all non-missing concern severity scores.

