#### 9.2.10 Behavior Problems Inventory-Short Form

The BPI-SF will be completed at Visit 3 (Week 0) and at the End of Treatment (Week 13, Visit 16). The BPI-SF is a caregiver-completed rating scale for assessing self-injury, aggressive and stereotyped behavior. Each item is measured for frequency and items in the Self-Injurious Behavior and Aggressive/Destructive Behavior subscales are also assessed for severity. The frequency is scored on a 5-point scale, where 0=never/no problem; 1=monthly, 2=weekly, 3=daily, 4=hourly. The severity is scored on a 3-point scale, where 1=mild, 2=moderate, 3=severe. The items are grouped in three subscales: Self-Injurious Behavior (score ranges from 0 - 32 for frequency and 8 - 24 for severity), Aggressive/Destructive Behavior (score ranges from 0 - 40 for frequency and 10 - 30 for severity), and Stereotyped Behavior (score ranges from 0 - 48 for frequency). The score for each subscale is the sum of the items within that domain. The total frequency score is the sum of the frequency scores for the three domains. The total severity score is the sum of the severity scores for Aggressive/Destructive Behavior and Self-Injurious Behavior subscales. The total severity and frequency scores will only be calculated if all contributing domain scores are not missing. Missing items will be imputed as defined in Section 5.2.5. A subscale score will only be calculated if all items in that domain are answered or can be imputed. Lower scores indicate lesser frequency and severity in behavior problems. Within subject change is the difference between the score at EOT and the score at baseline.

Summary statistics for the total score, subscale scores and their changes from baseline in the frequency and severity of BPI-SF scores will be displayed at End of Treatment. Within subject changes will be analyzed using a Wilcoxon signed rank test. The change from baseline in the total frequency and severity scores at EOT will be presented in plots as described in Section 9.2. The change from baseline in the subscale scores at EOT will be presented in a forest plot and waterfall plots. The subscale and total scores will be presented in line graphs at each visit.

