#### 9.2.11 Child Sleep Habits Questionnaire Scores

The CSHQ will be completed at all Screening/Baseline period visits (Visits 1, 2, 3), as well as Week 6 (Visit 9), End of Treatment (Week 13, Visit 16), and Follow-up (Visit 17). Each item is scored on a 3-point scale, where 1=rarely; 2=sometimes; 3=usually. Items 32 and 33 are scores as 1 = not sleepy, 2 = very sleepy and 3 = falls asleep. A higher score reflects more disturbed sleep behavior. The items are grouped into 4 domains and 8 subscale scores are derived from the items in these domains. The subscale scores are a sum of the items within that subscale, except for a few items which are reversed for scoring. Missing items will be imputed as defined in Section 5.2.5. The subscale scores will only be calculated if all items in the subscale are answered or can be imputed. The subscales and their corresponding items are listed below.

- Bedtime Resistance: Items 1, 3, 4, 5, 6, 8, where items 1 and 3 are reversed. Subscale score ranges from 6 18.
- Sleep Onset Delay: Item 2 where item 2 is reversed. Subscale score ranges from 1
   – 3.
- Sleep Duration: Items 9, 10, 11, where items 10 and 11 are reversed. Subscale score ranges from 3 9.
- Sleep Anxiety: Items 5, 7, 8, 21. Subscale score ranges from 4-12.
- Night Wakings: Items 16, 24, 25. Subscale score ranges from 3-9.
- Parasomnias: Items 12, 13, 14, 15, 17, 22, 23. Subscale score ranges from 7-21.
- Sleep Disordered Breathing: Items 18, 19, 20. Subscale score ranges from 3-9.
- Daytime Sleepiness: Items 26, 27, 28, 29, 30, 31, 32, 33, where item 26 is reversed. Subscale score ranges from 8-24.

The total score will be calculated as a sum of all 33 items, with items 1 - 3, 10 - 11, and 26 reversed. The total score will range from 33 - 99 and will only be calculated if all items are answered or can be imputed. Missing items will be imputed as defined in Section 5.2.5. Within subject change is the difference between the score at each relevant follow-up visit and the score at baseline.

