#### 9.2.14 Quality of Life Inventory - Disability (QI-Disability) Scores

The QI-Disability Score will be completed at Visit 3 (Week 0) and at the End of Treatment (Week 13, Visit 16). Each item is scored on a 5-point scale, where 1=never; 2=rarely; 3=sometimes; 4=often; 5=very often. The items are grouped into six domains for analysis: physical health (items 1-4), positive emotions (items 5-8), negative emotions (items 9-15), social interaction (items 16-22), leisure and the outdoors (items 23-27), and independence (items 28-32). The domain scores are calculated by first transforming the 5-point scale, so that 1=0, 2=25, 3=50, 4=75, and 5=100. Items 9-15 are reversed in scoring, so that 1=100, 2=75, 3=50, 4=25, and 5=0. The domain score is the average of the transformed score of the items within that domain. Missing items will be imputed as defined in Section 5.2.5. A domain score will be calculated as long as at least one of the items within the domain is answered. The overall score is the average of all domain scores and will be calculated as long as at least one of the domain scores can be calculated. Higher scores indicate a better quality of life. Within subject change is the difference between the score at EOT and the score at baseline.

Summary statistics for the change from baseline in the QI-Disability overall and domain scores will be displayed at end of treatment. Changes from baseline will be analyzed using a Wilcoxon signed rank test. The change from baseline in the overall score at EOT will be presented in plots as described in Section 9.2. The change from baseline in the domain scores at EOT will be presented in a forest plot. The domain and overall scores will be presented in line graphs at each visit.

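### Carrying forward up to three missing items, whatever the scale length, enters pre-treatment answers as EOT data for BPI-SF and QI-Disability and lets five short CSHQ and GIHQ subscales be scored with no item observed at that visit

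*SAP*

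**What the plan says.** SAP 5.2.5 (Post-Baseline Values) covers a rating scale that was completed but has blank items: "If 3 or fewer items are missing, the last observation for that particular data element (e.g., item response) will be carried forward". The count applies to the assessment as a whole. No minimum number of answered items is set for a scale or subscale. The section confines the rule to single items and adds: "Total scores, subdomain and subscale scores will not be carried forward". SAP 9.2 says: "There will be no imputations for completely missing scores or intercurrent events". CGI-I, CGI-S, Caregiver Impression of Change and Top 3 Concerns are exempt.

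BPI-SF (SAP 9.2.10, restated in the addendum) adopts the rule: "Missing items will be imputed as defined in Section 5.2.5". QI-Disability (9.2.14) points to the same section. Both are collected at Visit 3, before the first dose, and at EOT, with nothing between. A QI-Disability domain is the average of its items and is scored even if only one was answered.

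CSHQ (9.2.11) and GIHQ (9.2.12) also use the rule. They are collected at Visits 1, 2 and 3, Week 6, EOT and Follow-up, and a subscale is scored when every item is either answered or imputable. One CSHQ subscale is a single item: "Sleep Onset Delay: Item 2 where item 2 is reversed". Three more (Sleep Duration, Night Wakings, Sleep Disordered Breathing) have three items, as does GIHQ Reflux. For scales rated at several pre-dose visits, SAP 5.2.4 takes the average as baseline. The addendum does not change 5.2.5.

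**The concern.** Two separate problems follow, mostly in different instruments.

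(a) For BPI-SF and QI-Disability, the only observation before EOT is the pre-treatment one. A carried item therefore contributes a change of exactly zero, which is then summarised and tested as if observed. This pulls the score toward no change in either direction, so a worsening in self-injury or aggression is muted as much as an improvement. With 10 to 20 participants planned, one affected child is 5 to 10% of the sample.

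(b) For the five short CSHQ and GIHQ subscales, all items may be blank at a visit and the subscale is still scored. When every item is carried, the recomputed score equals the previous one. In effect a subscale score has been carried forward, which goes against the evident intent of the two limiting sentences in 5.2.5 and 9.2.

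**Working it through.** **Item counts, checked against the SAP's score ranges.** Items are scored 0–4 (BPI-SF and GIHQ frequency), 1–3 (BPI-SF severity, CSHQ).

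- BPI-SF frequency: 32/4 = 8 self-injury items, 40/4 = 10 aggression, 48/4 = 12 stereotyped. Severity agrees: 24/3 = 8 and 30/3 = 10. Totals: 8 + 10 + 12 = 30 frequency items; 8 + 10 = 18 severity items.
- CSHQ: range 1–3 for one item, 3–9 for three items, 33–99 for the 33-item total. All match.
- GIHQ Reflux frequency: 3 × 4 = 12, matching 0–12.
- QI-Disability, from the listed item numbers: domains of 4, 4, 7, 7, 5 and 5 items, 32 in all.

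**(a) Pre-treatment items carried to EOT.** Let a score have m items, each with the same true change d, and let k = min(3, m) be carried from baseline. True change is m·d, measured change is (m − k)·d, so the share lost is k/m.

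| Score | m | Lost with 3 carried | Retained |
|---|---|---|---|
| QI-Disability Physical Health; Positive Emotions | 4 | 75% | 25% |
| QI-Disability Leisure; Independence | 5 | 60% | 40% |
| BPI-SF self-injury | 8 | 37.5% | 62.5% |
| BPI-SF aggression | 10 | 30% | 70% |
| BPI-SF stereotyped | 12 | 25% | 75% |
| BPI-SF total severity | 18 | 16.7% | 83.3% |
| BPI-SF total frequency | 30 | 10% | 90% |
| QI-Disability, share of all items | 32 | 9.4% | 90.6% |

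The QI-Disability overall score averages six domains equally, so three carried items in one four-item domain cost 0.75/6 = 12.5% of it.

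**QI-Disability at the threshold.** Illustration: every item moves from 50 to 75, a true domain change of 25.

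- Three items blank, all in one four-item domain: EOT = (75 + 50 + 50 + 50)/4 = 56.25, so the measured change is 6.25, or 25% of the truth.
- A fourth item also blank in another domain: the limit is exceeded and nothing is carried. The first domain is scored from its one answer: EOT = 75, change = 25.

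An extra missing answer elsewhere thus removes the bias in this example, which is the wrong way round for a missing-data rule.

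**(b) Whole subscales from carried items.** The share min(3, m)/m is 1/1 for Sleep Onset Delay and 3/3 for Sleep Duration, Night Wakings, Sleep Disordered Breathing and GIHQ Reflux. This is the share of the score that is carried. It is not the share of change lost, because the source of the carried value differs by visit:

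- EOT analysis: normally the Week 6 answer, given on treatment. It is pre-treatment only if the Week 6 item is also blank.
- Week 6 analysis: a pre-treatment answer. Baseline is the average of the pre-dose visits, so the resulting change is near zero but not exactly zero.

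In the CSHQ and GIHQ totals, three items are 3/33 = 9.1% and 3/55 = 5.5%.

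**The case against.** A reader might infer that 5.2.5 contradicts itself. Read literally it does not: it allows items to be carried and bars carrying scores. The 9.2 sentence can also be read as already excluding a wholly unanswered subscale. What stands is that neither sentence says so, while the scoring rules in 9.2.11 and 9.2.12 accept a subscale whose items are all imputed.

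A reader might also infer that the short subscales lose 100% of their EOT change. The documents do not support that, because CSHQ and GIHQ have a Week 6 visit and an averaged baseline.

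On frequency, whole-subscale carry should be rare. If exactly three CSHQ items were blank at random (an assumption), the chance that they fill one three-item subscale is 3/5456, about 0.05%; for GIHQ Reflux it is 1/26235. Skipped blocks would raise this, and Sleep Onset Delay needs only one blank. Protocol 13.2 and 13.3 also call for complete forms and central completeness checks. For Reflux, 5.2.5 leaves unclear whether a question left blank on frequency, relevancy and importance counts once or three times.

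On consequence, the tests are descriptive, there is no primary efficacy endpoint, and safety data are not imputed. Shrinkage toward zero is conservative for a claim of benefit. All of this limits the size of the problem. None of it supports treating a pre-treatment answer as an EOT answer.

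Finally, one might say that a section headed Post-Baseline Values means only post-baseline answers are carried. It does not say so, and on that reading the references to 5.2.5 under BPI-SF and QI-Disability would have nothing to act on.

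**Conclusion.** The concern holds in two parts. (a) For BPI-SF and QI-Disability, every item carried to EOT is by design the pre-treatment answer with zero change. Three carried items remove up to 37.5% of change in BPI-SF self-injury, 30% in aggression, 75% in a four-item QI-Disability domain and about 9 to 17% in the totals. (b) Four CSHQ subscales and GIHQ Reflux can be scored with no item observed at the visit, which carries a subscale score forward in effect though not in wording.

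The percentages are worst cases: three items missing, all in the score concerned, and equal true change across items. The documents give no item-missingness rate, so the actual effect cannot be computed. For secondary, descriptive endpoints it is probably small. The rule merits correction because it is biased as written and cheap to replace.

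**What to change.** In SAP 5.2.5, replace item carry-forward with same-visit proration within the subscale: mean of answered items times number of items, or simply the mean where the score is an average. Apply it when at least half the subscale's items are answered; otherwise set the subscale to missing. State that this minimum replaces the one-answered-item rule for QI-Disability domains in 9.2.14. Averaging what was answered is already the SAP's approach for QI-Disability and Top 3 Concerns.

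Add a sentence on totals. The addendum already requires all contributing BPI-SF domains to be present. For CSHQ, items 5 and 8 belong to two subscales but count once in the total, so say how prorated values enter it.

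At a minimum, bar pre-treatment answers from post-baseline visits and do not score a subscale with no observed item.

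Cost: SAP wording, a change to the scoring programs, and a few short subscales becoming missing. Proration also assumes that items within a subscale are roughly exchangeable, which is open to doubt for distinct behaviours such as those in BPI-SF self-injury. The half-answered minimum limits that risk without removing it.
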